**Notes:**

- **Group A:** Azacitidine 75 mg/ m² SC or IV on D1 through D7, cusatuzumab 10 mg/kg IV on Day 3 and 17 of each 28 day cycle.
- **Group B:** Azacitidine 75 mg/ m² SC or IV on D1 through D7, cusatuzumab 20 mg/kg IV on Day 3 and 17 of each 28 day cycle.
- Number of participants (n) at each Stage of Part 1 and Interim and Final Analyses are cumulative.

1.3. Statistical Hypothesis for Trial Primary Objective

The primary hypothesis is that participants treated with the combination of cusatuzumab (at a dose level of 10 mg/kg or 20 mg/kg) and azacitidine can achieve a CR rate of 35% or greater against the null hypothesis of 20%.

1.4. Sample Size Justification

Up to 50 participants will be randomized into each dose group in Part 1 of the study to select a dose and continue into Part 2. Participants will be enrolled into Part 2 at the selected dose until a cumulative total of 100 participants have been treated with the selected dose from Part 1 and Part 2. The study has a >90% power to reject the null hypothesis of a CR rate of 20% under the alternative hypothesis of 35%. This sample size is based on the single-arm Wilson Score test without continuity correction at an overall 1-sided type 1 error rate <2.5%.

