9.2. Sample Size Determination

Up to 50 participants will be enrolled for each dose group in Part 1 of the study. Part 1 will utilize a 3-stage monitoring approach to determine, at each stage and for each dose group, if the observed CR rate warrants the respective dose to be continued into the next stage or into Part 2 of the study (see details in Section 9.5, Interim Analysis). Participants will be enrolled into Part 2 at the selected cusatuzumab dose until a cumulative total of 100 participants have been treated with the selected dose from Part 1 and Part 2. The study has a >90% power to reject the null hypothesis of a CR rate of 20% under the alternative hypothesis of 35% for a total of 100 participants (from Part 1 and Part 2) at the selected dose level. This sample size is based on the single-arm Wilson Score test without continuity correction at an overall 1-sided type 1 error rate <2.5%.

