9.5. Interim Analyses

For each analysis (3 stages in Part 1 and the formal interim and final analysis in Part 2), the data cutoff will be the time point when the last participant in the respective analysis has been treated for a minimum of 3 cycles (Part 1) or 4 cycles (Part 2) of the combination therapy.

NOTE: Part 2 of the study will not be conducted because further development of this regimen (cusatuzumab in combination with azacitidine) in patients with unfit AML will not be pursued due to the evolving treatment landscape in AML.

Study Part 1

Part 1 of the study consists of 3 stages of monitoring to select a dose schedule. The cumulative number of participants for each dose group at each of the 3 stages are 15, 30, and 50, respectively. At each stage, each dose group's response rate will determine independently (without formal statistical comparison to the other group) if that dose group will be stopped or continued into the next stage or into study Part 2. Only 1 dose group will be selected for Part 2. The statistical criteria for such a determination will be based on the number (and percentage) of participants in each dose group achieving CR.

The purpose of the 3-stage monitoring in Part 1 is to select, or to eliminate a dose, which will be based on the Pocock beta-spending function with an overall beta level of 10% allocated to the 3 stages with respective and cumulative sample sizes of 15 (30%), 30 (60%), and 50 (100%) participants per group. Per this approach, the statistical decision criteria and corresponding inferences are summarized in Table 7, where 2 possible outcomes resulting in a stop or continuation decision, respectively, are presented for each stage.

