1.5. Interim Analyses

For each analysis (3 stages in Part 1 and the formal interim and final analysis in Part 2), the data cutoff will be the time point when the last participant in the respective analysis has been treated for a minimum of 3 cycles (Part 1) or 4 cycles (Part 2) of the combination therapy.

Study Part 1

Part 1 of the study consists of 3 stages of monitoring to select a dose schedule. The cumulative number of participants for each dose group at each of the 3 stages are 15, 30, and 50, respectively. At each stage, each dose group's response rate will be determined independently (without formal statistical comparison to the other group) if that dose group will be stopped or continued into the next stage or into study Part 2. Only 1 dose group will be selected for Part 2. The statistical criteria for such a determination will be based on the number (and percentage) of participants in each dose group achieving CR.

The purpose of the 3-stage monitoring in Part 1 is to select, or to eliminate a dose, which will be based on the Pocock beta-spending function. The overall beta level is chosen as 10%, allocated to the 3 stages with respective and cumulative sample sizes of 15 (30%), 30 (60%), and 50 (100%) participants per group; the corresponding nominal significance level (calculated against the alternative hypothesis of 35% CR rate) are 0.04157, 0.04618, and 0.05632. Per this approach, the statistical decision criteria and corresponding inferences are summarized in [Table 1](#), where 2 possible outcomes resulting in a stop or continuation decision are presented for each stage.

The statistical criteria shown in [Table 1](#) ensure that the false negative error rate (ie, the probability of a stopping decision, when the true CR rate is $\geq 35\%$) is $\leq 6\%$ at any stage; or equivalently, the upper limit of the 1-sided $>94\%$ confidence interval (CI) of the observed CR rate is $<35\%$ (which means that a CR rate of 35% or greater has been statistically ruled out). It's important to control the false negative error rate at a low level when the number of participants is small to ensure that a stopping decision will not be made unless it is statistically convincing that a CR rate of $\geq 35\%$ has been ruled out. Since all the analyses in study Part 1 are futility evaluations without the intention to stop for efficacy, the overall type I error of the entire study is not inflated.

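### The >90% power in SAP 1.4 leaves out the Part 1 futility stops; if that guidance is followed at all three stages, a given dose with a true CR rate of 35% has about 83% power

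*SAP*

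**What the plan says.** SAP 1.4 gives the power claim: "The study has a >90% power to reject the null hypothesis of a CR rate of 20% under the alternative hypothesis of 35" per cent. Its basis follows: "This sample size is based on the single-arm Wilson Score test without continuity correction at an overall 1-sided type 1 error rate <2.5" per cent. Enrolment at the chosen dose runs until "a cumulative total of 100 participants have been treated with the selected dose from Part 1 and Part 2".

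Protocol 9.2 and the protocol synopsis make the same claim but add a qualifier that SAP 1.4 lacks: "for a total of 100 participants (from Part 1 and Part 2) at the selected dose level".

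SAP 1.5 then describes the looks that come before that test. "The cumulative number of participants for each dose group at each of the 3 stages are 15, 30, and 50, respectively". On the error spent there, it says "The overall beta level is chosen as 10%, allocated to the 3 stages"; Protocol 9.5 agrees ("Pocock beta-spending function with an overall beta level of 10% allocated to the 3 stages"). The nominal levels against a 35% CR rate "are 0.04157, 0.04618, and 0.05632". SAP Table 1 (Protocol Table 7) turns these into stops at 2 or fewer CRs of 15, 6 or fewer of 30, and 12 or fewer of 50. Both documents call these criteria guidance.

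SAP 1.5 discusses what the Part 1 looks do to the type I error and concludes that it is not inflated. Neither document says what they do to power.

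**The concern.** A futility look leaves the type I error alone or lowers it, but it costs power. A dose with a true 35% rate has to survive Part 1 and then succeed in Part 2, and the two losses add. If 10% is spent in Part 1 on stopping such a dose, its overall power cannot exceed 90% even if Part 2 never missed. SAP 1.4 and SAP 1.5 therefore cannot both describe the same dose under the same rules.

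What is at stake is how the sample size justification is read. A reader of SAP 1.4 would take the chance of missing an active dose to be under 10%. With the stops followed it is 16.6%, about twice the 8.0% of the no-stop design.

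**Working it through.** **Inputs.** Null 20%, alternative 35%, n = 100, Wilson score test without continuity correction (SAP 1.4). Looks at 15, 30 and 50 with the stops above (SAP Table 1). Part 2 tests at n = 80 (one-sided p ≤ 0.01221) and n = 100 (p ≤ 0.02144) (SAP 1.5). No dropout allowance is stated, and none is used.

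**Part 2 cut-offs.** z = (x/n − 0.20) / √(0.20 × 0.80 / n).
- 25/80: z = 0.1125/0.0447 = 2.52, p = 0.0059, rejects. 24/80: z = 2.24, p = 0.0127, does not.
- 29/100: z = 0.09/0.04 = 2.25, p = 0.0122, rejects. 28/100: z = 2.00, p = 0.0228, does not.

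The rule is therefore ≥25/80, otherwise ≥29/100.

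**The plan's own figure.** The exact binomial calculation with no Part 1 stops, at a 35% CR rate, gives 79.3% (rejection at 80) + 12.7% (first rejection at 100) = **92.0%**. The exact type I error at 20% is 2.31%. The stated >90% and <2.5% both reproduce.

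**With the stops.** Carry the distribution of the CR count forward through 15, 30, 50, 80 and 100, removing stopped paths at each Part 1 look:

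| Step, true CR rate 35% | Probability |
|---|---|
| Stop at Stage 1 (≤2/15) | 6.17% |
| Stop at Stage 2 (≤6/30) | 3.35% |
| Stop at Stage 3 (≤12/50) | 3.12% |
| Total stopped in Part 1 | 12.6% |
| Pass Part 1 | 87.4% |
| Pass and reject at 80 | 74.5% |
| Pass and first reject at 100 | 8.8% |
| **Overall power for this dose** | **83.4%** |

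Conditional on passing Part 1, power is 0.8337/0.8735 = 95.4%. With the Stage 1 look alone it is 87.3%.

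**Why 12.6% and not 10%.** The three nominal levels give 10.0% total stopping on the normal scale, as designed. The exact binomial tails at the whole-number boundaries are larger: at Stage 1, for example, P(X ≤ 2) is 6.17% against 3.93% by the normal approximation.

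**Cross-check.** Protocol Table 8 gives 98.4% for at least one of two 35% doses continuing. For independent arms, √(1 − 0.984) = 12.6% stopping per dose, which matches.

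**Study level.** Two independent arms were simulated with 1,000,000 runs per case. The documents state no numerical selection rule, so the higher CR count at n = 50 is assumed to be chosen, with ties at random. Each range runs from Protocol 9.5 (all looks applied) to Protocol 4.1 (once one dose is dropped at Stage 1 or 2, the other skips its remaining Part 1 looks).

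| One dose 35%, other dose | Selected dose rejects | 35% dose is selected and rejects |
|---|---|---|
| 20% | 82.7% to 84.6% | 82.0% to 84.0% |
| 30% | 90.2% to 91.3% | not used here |
| 35% | 96% to 97% | about 48% for each dose |

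**The case against.** Four points count on the other side.

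1. Protocol 9.2 and the synopsis limit the claim to 100 participants at the selected dose. On that reading it is 92.0% as a fixed design, or 95.4% given passage through Part 1, and both exceed 90%. This stands for the protocol. SAP 1.4 names the selected dose in the preceding sentence, but its power sentence carries no such limit.
2. The Part 1 criteria are guidance, and the decision rests on all the data. This stands: 83.4% assumes the stops are followed at all three stages. The direct-continuation rule in Protocol 4.1 can also spare a dose the later looks. Every dose still faces Stage 1, and that look alone brings power to 87.3%.
3. Table 8 already discloses the Part 1 losses. It does, for Part 1 alone. Neither document combines them with the Part 2 test.
4. Part 2 was not conducted, and SAP 1.6 plans no hypothesis test. This stands and limits the consequence.

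A reader might infer that the 10% Part 1 beta rules out more than 90% power for the study as a whole. The documents do not support that. The hypothesis covers either dose, and the chance that the selected dose rejects is above 90% when the other dose is 30% or 35%. The 90% ceiling applies to one given dose. Nor should 83% to 85% be quoted as study power when the other dose is at 20%: that range counts rejections for the 20% dose, which is at the null.

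**Conclusion.** The concern holds for a given dose. SAP 1.4 states as a property of the study a power that leaves out the study's own Part 1 stops. At a true CR rate of 35%, power is 92.0% without the stops and 83.4% with all three followed, a loss of 8.6 points. If only the Stage 1 look applies, it is at most about 87%.

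The >90% figure remains true in three cases: the stops are not applied; it is read as conditional on the selected dose; or both doses are active. SAP 1.4 states none of these conditions.

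The per-dose figures are exact and rest on the tabulated boundaries, the planned sample sizes and no dropout. The two-dose figures also rest on independent arms and the assumed selection rule. With Part 2 cancelled, the error lies in the stated design property. No planned final analysis depends on it.

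**What to change.** In SAP 1.4, and as a clarification in Protocol 9.2 and the synopsis, replace the power sentence with:

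> About 92% power for 100 participants at the selected dose, not counting the Part 1 stops; about 83% for a given dose with a true CR rate of 35% if the Part 1 stopping guidance is followed at all three stages.

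If a study-level figure is wanted with the other dose at 20%, give 82% to 84% that the 35% dose is selected and rejects, and state the assumed selection rule (higher CR count, ties at random). Add that Part 2 was not conducted and that SAP 1.6 plans descriptive summaries only.

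The cost is one sentence in each of three places and a less favourable figure. No boundary, sample size or analysis changes.

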1.5. Interim Analyses

For each analysis (3 stages in Part 1 and the formal interim and final analysis in Part 2), the data cutoff will be the time point when the last participant in the respective analysis has been treated for a minimum of 3 cycles (Part 1) or 4 cycles (Part 2) of the combination therapy.

Study Part 1

Part 1 of the study consists of 3 stages of monitoring to select a dose schedule. The cumulative number of participants for each dose group at each of the 3 stages are 15, 30, and 50, respectively. At each stage, each dose group's response rate will be determined independently (without formal statistical comparison to the other group) if that dose group will be stopped or continued into the next stage or into study Part 2. Only 1 dose group will be selected for Part 2. The statistical criteria for such a determination will be based on the number (and percentage) of participants in each dose group achieving CR.

The purpose of the 3-stage monitoring in Part 1 is to select, or to eliminate a dose, which will be based on the Pocock beta-spending function. The overall beta level is chosen as 10%, allocated to the 3 stages with respective and cumulative sample sizes of 15 (30%), 30 (60%), and 50 (100%) participants per group; the corresponding nominal significance level (calculated against the alternative hypothesis of 35% CR rate) are 0.04157, 0.04618, and 0.05632. Per this approach, the statistical decision criteria and corresponding inferences are summarized in [Table 1](#), where 2 possible outcomes resulting in a stop or continuation decision are presented for each stage.

The statistical criteria shown in [Table 1](#) ensure that the false negative error rate (ie, the probability of a stopping decision, when the true CR rate is $\geq 35\%$) is $\leq 6\%$ at any stage; or equivalently, the upper limit of the 1-sided $>94\%$ confidence interval (CI) of the observed CR rate is $<35\%$ (which means that a CR rate of 35% or greater has been statistically ruled out). It's important to control the false negative error rate at a low level when the number of participants is small to ensure that a stopping decision will not be made unless it is statistically convincing that a CR rate of $\geq 35\%$ has been ruled out. Since all the analyses in study Part 1 are futility evaluations without the intention to stop for efficacy, the overall type I error of the entire study is not inflated.

If the number of participants at each stage is not exactly as specified in [Table 1](#), the Pocock beta-spending function with an overall beta level of 10% will be adjusted based on the actual number participants.

The above statistical criteria for Part 1 will be served as guidance; the totality of the data including other efficacy outcomes (eg, duration of CR), available safety, and PK/PD data will be considered in making a decision at each stage. If both dose schedules warrant proceeding into Part 2 per the above statistical criteria, only one dose schedule will be extended into Part 2 based on the observed CR rate as well as available data of other efficacy, safety, and PK/PD.

Table 1: Statistical Decision Parameters for Study Part 1: Observed CR, 1-Sided Confidence Interval (CI), and Statistical Decision

	Number (%) of Observed CR	1-Sided CI Upper Bound ¹ (%)	Decision	False Negative Error ²	False Positive Error ³
Stage 1, n=15	1 (6.7)	26.7	Stop	≤4%	NA
	2 (13.3)	34.9			
	3 (20.0)	42.3	Continue to Stage 2	NA	≤50%
	4 (26.7)	49.3			
Stage 2, n=30	5 (16.7)	30.5	Stop	≤5%	NA
	6 (20.0)	34.3			
	7 (23.3)	37.9	Continue to Stage 3	NA	≤32%
	8 (26.7)	41.5			
Stage 3, n=50	11 (22.0)	32.3	Stop	≤6%	NA
	12 (24.0)	34.4			
	13 (26.0)	36.6	Continue to Part 2	NA	≤14%
	14 (28.0)	38.7			

¹ 96%, 95%, and 94% for Stage 1, 2, and 3, respectively.

² False negative error: probability of a “stop” decision, when the true CR rate is ≥35%.

³ False positive error: probability of a “continue” decision, when the true CR rate is ≤20%.

Note: All statistical inferences are based on Wilson Score statistics without continuity correction.

Study Part 2

For Part 2, 1 interim analysis of CR rate is planned to include 80 participants. The null hypothesis of a CR rate of 20% will be rejected if the 1-sided nominal p-value is ≤0.01221. If the null hypothesis is not rejected at this interim analysis, the final analysis will be performed with 100 participants, and the null hypothesis will be rejected if the 1-sided nominal p-value is ≤0.02144. The O’Brien-Fleming alpha-spending, and Wilson Score test without continuity correction is to be implemented for the interim and final analyses.

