Part 1 of the study utilizes a 3-stage monitoring approach as the statistical guidance to select a dose schedule (see Section 9.5, Interim Analysis). The cumulative number of participants for each dose group at each of the 3 stages are 15, 30, and 50, respectively. Response will be based on all evaluations up to the time point when the last participant is treated for a minimum of 3 cycles with combination therapy (cusatuzumab + azacitidine). At each stage, available data of efficacy, safety, pharmacodynamics, and biomarkers will be evaluated by a Data Review Committee (DRC) to determine if either or both of these treatment groups should continue into the next stage of Part 1, and by the end of Part 1 (n=50/group), to select 1 dose schedule to be continued into study Part 2. The DRC will be formed prior to the first participant being enrolled in the trial and will remain in place until the conclusion of the trial. Enrollment does not pause at each stage. Refer to Committees Structure in Appendix 3 (Section 10.3), Regulatory, Ethical, and Study Oversight Considerations for details.

If, based upon the totality of the data, 1 treatment group is considered to be less effective at any stage of Part 1, then that treatment group will be closed to enrollment. Upon 1 dose level being selected to continue, the DRC may determine to switch ongoing participants to treatment with the dose level selected. If 1 dose group is determined at Stage 1 or Stage 2 not to continue, the other dose group will be continued into study Part 2 directly without further evaluations in Part 1. Enrollment will continue at each of the above 3 stages while efficacy and safety data are accumulated and evaluated.

Additionally, after 5, 15, 30, and 50 participants have enrolled on each arm, respectively, and been treated for 3 cycles, cumulative safety data will be evaluated by the DRC to ensure continued study treatment is safe.

Part 2:

For Part 2, the treatment group to be studied will be dependent upon the results from Part 1. At the end of Part 1, all available data will be evaluated by the DRC to select 1 of the cusatuzumab treatment groups for further evaluation in Part 2.

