1.6. Changes of Study Conduct and Planned Analyses

The study did not proceed into Part 2 per decision by study Sponsor and the DRC upon completion of the analyses in all 3 stages in study Part 1. Data from study Part 1 will be summarized with descriptive statistics without formal comparison or hypothesis testing.

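### Does choosing one of two doses partly on CR rate undercut the SAP's statement that the study-wide type I error is not inflated?

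*SAP*

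**What the plan says.** SAP 1.5 sets three futility looks in Part 1 (15, 30 and 50 participants per dose) and concludes that "the overall type I error of the entire study is not inflated". On the stopping rules it adds: "The above statistical criteria for Part 1 will be served as guidance". If both doses qualify, "only one dose schedule will be extended into Part 2 based on the observed CR rate", together with other efficacy, safety and PK/PD data.

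SAP 1.3 states the hypothesis for either dose: "cusatuzumab (at a dose level of 10 mg/kg or 20 mg/kg) and azacitidine can achieve a CR rate of 35% or greater", against a null of 20%. SAP 1.4 continues enrolment "until a cumulative total of 100 participants have been treated with the selected dose from Part 1 and Part 2", and gives power above 90% and an overall one-sided error below 2.5% for a single-arm Wilson score test. SAP 1.5 tests at 80 participants (nominal p ≤ 0.01221) and at 100 (nominal p ≤ 0.02144).

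Protocol 4.1 adds that if one dose is dropped at Stage 1 or 2, "the other dose group will be continued into study Part 2 directly without further evaluations in Part 1".

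SAP 1.6 then reports that the study did not go on to Part 2, and states: "Data from study Part 1 will be summarized with descriptive statistics without formal comparison or hypothesis testing".

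**The concern.** Futility looks alone cannot raise the type I error for one dose; if they are obeyed, they lower it. Part 1 does more than screen for futility, however. It chooses between two doses, the primary endpoint feeds the choice, and the data that drove the choice count again in the final test. The hypothesis covers either dose, so a false success at either one is an error of the study. Neither document adjusts the 2.5% for this, and Protocol Table 8 gives operating characteristics for Part 1 only.

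Had the n=80 and n=100 tests been run, a reader could have taken the 2.5% to cover the choice of dose when it did not. A lesser point is that SAP 1.4 still quotes the power and error of the 100-participant test without pointing to SAP 1.6.

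**Working it through.** **Inputs.** Null 20%, alternative 35%, nominal levels 0.01221 (n=80) and 0.02144 (n=100), Wilson score test without continuity correction (SAP 1.3 to 1.5). Part 1 stops at ≤2/15, ≤6/30 and ≤12/50 CRs (SAP Table 1).

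**Step 1: the plan's own figures.** O'Brien-Fleming-type spending of 0.025 with the interim at 80/100 gives nominal levels 0.012212 and 0.021435, as stated. The score statistic is z = (x/n − 0.20)/√(0.20 × 0.80/n).

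- n=80: 25 CRs give z = 2.516, p = 0.0059 (reject); 24 give z = 2.236, p = 0.0127 (do not reject).
- n=100: 29 CRs give z = 2.250, p = 0.0122 (reject); 28 give z = 2.000, p = 0.0228 (do not reject).

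The critical counts are therefore 25/80 and 29/100. Exact binomial calculation over the two looks, for one named dose without stops, gives error 2.31% at 20% and power 92.0% at 35%. Both agree with SAP 1.4.

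**Step 2: one named dose, stops followed.** A dose passes all three stages with probability 0.8735 at 35% and 0.1501 at 20%. As a check, 1 − (1 − 0.8735)² = 98.4%, which is the Protocol Table 8 entry. The error falls to 1.78%. For a given dose the SAP's argument is correct.

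**Step 3: two doses, both truly 20%.** The documents give no algorithm for the pick, so it is bracketed between a pick unrelated to CR and a pick of the higher CR count (ties at random).

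- *Stops followed, each dose judged independently, random pick if both survive.* A dose that would succeed is carried forward whenever the other stops (0.8499), and half the time when the other survives (0.1501). The error is 0.01778 × (2 × 0.8499 + 0.1501) = 0.01778 × 1.8499 = 3.29%. Picking the higher CR gives 3.42%.
- *Stops followed, direct-continuation rule of Protocol 4.1.* 3.60% (random) and 3.73% (higher CR).
- *Stops not followed, pick unrelated to CR.* 2.31%, the single-dose figure.
- *Stops not followed, higher CR picked at n=50.* Let f and F be the probability and cumulative probability of x CRs in 50, and R(x) the chance of later rejection. Then Σ f(x)[2F(x) − f(x)]R(x) = 4.23%.
- *Stops not followed, CR decides a quarter of the time.* 0.75 × 2.31% + 0.25 × 4.23% = 2.79%.

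**Step 4: other true rates** (random pick / higher CR picked).

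| True CR rates | Stops followed, independent | Stops followed, direct rule | Stops not followed |
|---|---|---|---|
| 20%, 20% | 3.29% / 3.42% | 3.60% / 3.73% | 2.31% / 4.23% |
| 20%, 19% | 2.53% / 2.62% | 2.78% / 2.88% | 1.76% / 3.27% |
| 20%, 18% | 2.12% / 2.17% | 2.33% / 2.40% | 1.44% / 2.73% |
| 20%, 17% | 1.91% / 1.94% | not computed | 1.28% / 2.46% |
| 20%, 15% | 1.78% / 1.80% | 2.00% / 2.03% | 1.17% / 2.31% |
| 19%, 19% | 1.75% / 1.80% | 1.92% / 1.98% | 1.21% / 2.25% |

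When the two true rates are equal, the rules that can exceed 2.5% do so only above about 19.2% to 19.6%.

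**Step 5: what uses these figures.** They all concern the tests at 80 and 100 participants. SAP 1.6 says those tests were not reached and that no hypothesis test is made on Part 1.

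**The case for a change.** The case for a change is that the sentence is too broad as written. Its premise concerns futility looks for one dose; its conclusion concerns the whole study. Type I error is judged at the null, the null is 20%, and Protocol Table 8 itself uses the scenario with both doses at 20%. Even a purely random pick gives 3.3% if the stops are followed, because a second dose gets its own chance whenever the first is eliminated. Limiting the claim to a given dose would take a few words.

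The overreach in wording stands, and so do the figures. Three things limit its weight.

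- The top figure of 4.2% needs every stop set aside and the pick made on CR alone, whereas the plan describes a judgement on all the data. Nor is 3.3% a floor once CR plays some part: the 2.8% above is a counter-example.
- Protocol 9.2 ties the sample size to the selected dose level and to a single-arm test. Read dose by dose, the 2.5% is correct.
- The trial ended before either test.

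A pointer in SAP 1.4 would add nothing either. Its two figures reproduce for the test they describe, SAP 1.6 already says that Part 2 did not take place, and the protocol repeats the cancellation in several sections, including 1.1, 4.1 and 9.5. Power for one dose is 83.4% if the stops are followed, but this contradicts nothing in SAP 1.4, which describes one dose taken to 100.

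**Conclusion.** No change is needed. The sentence in SAP 1.5 is right about the futility looks and too broad about the study. At exactly 20% for both doses, the study-wide error would have been between 2.3% and 4.2%, at most about 1.7 points above the nominal 2.5% (4.2 − 2.5). The excess fades within a point or so when both rates drop together: at 19% for both it is gone under every rule examined. With one dose held at 20%, it is gone once the other is at 17% under the rules computed there.

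The figures assume independent arms, exactly 15/30/50/80/100 participants, a pick that does not run against CR, no switching between doses, and no change in CR status between the 3-cycle and 4-cycle cutoffs.

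What settles the point is SAP 1.6: the tests were not run and Part 1 is descriptive, so neither a rewording of SAP 1.5 nor a note in SAP 1.4 would alter anything the trial does, reports or concludes.
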